##### Liver function:

- Mean change from Baseline in serum ALT, AST, bilirubin, albumin and GGT at Weeks 4, 8, 12, 16, 20 and 24
- Proportion of subjects whose ALT at Week 24 is within reference range defined a  $\leq 19$  IU/L for women and  $\leq 30$  IU/L for men
- The proportion of subjects demonstrating a decrease in serum ALT at 24 weeks compared to baseline equal or greater than 30% compared to placebo

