Serum lipid profile values of total cholesterol, triglycerides and high and low density lipoproteins with change from Baseline and number of clinically significant values will be summarised and tabulated by visit and treatment group. Liver function values of ALT, AST, GGT, bilirubin and albumin, with change from Baseline will be summarised and tabulated by visit and treatment group. These liver function tests will also be correlated with HFF, CRP, and A1c. The proportion of subjects with ALT within the normal reference range at Week 24 will be summarised and tabulated by treatment group. Logistic regression modelling will be used to compare proportions in the Placebo group against each of the IMM-124E treatment dose groups using the same model used in the primary efficacy analysis, although the Baseline value of the liver function analyte will be used as a covariate. The area under the curve for change

from Baseline to Week 24, using the Baseline value as reference, for liver enzymes ALT, AST and GGT will also be analysed. For patients in the FAS population who withdraw prior to Week 24, the area under the curve will be adjusted in a manner comparable to a full 24 week period value.

The proportion of subjects demonstrating a decrease in liver percent fat at 24 weeks compared to baseline of 5%, 10%, 20% and 30% respectively will also be analysed. In a similar manner, proportional decreases in ALT, AST and A1c will be assessed using appropriate percentages.

Correlations between change in hepatic fat fraction and changes in ALT, C-reactive protein and A_{1c} will also be calculated.

The Fibrosis-4 Score will be calculated at each visit for which there is data. The formula is $FIB-4 = (Age * AST) / (Platelets / \sqrt{ALT})$. This score will be summarised and tabulated in the same manner as the primary endpoint.

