8.5 Laboratory safety measurements

Serum biochemistry parameters will be summarised with change from Baseline and the count of clinically significant values and tabulated by visit. If multiple units are reported in the eCRF, values will be transformed to SI units prior to summary. Additionally, a serum biochemistry shift table, showing the number of normal values, abnormal (both above and below normal range) but not clinically significant, clinically significant (both above and below normal range) at Baseline and each visit during the treatment and follow-up periods will also be produced. Parameters summarised and tabulated in lipid panel, biomarkers and regulatory T cell tables will be excluded.

Haematology parameters will be summarised with change from Baseline and the count of clinically significant values and tabulated by visit. Additionally, a haematology shift table, showing the number of normal values, abnormal (both above and below normal range) but not clinically significant clinically significant (both above and below normal range) at Baseline and each visit during the treatment and follow-up periods will also be produced.

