C-reactive protein with change from Baseline by visit with Fibrosis sub-groups as stratification factor (PP population)

C-reactive protein with change from Baseline by visit with Ballooning sub-groups as stratification factor (FAS population)

C-reactive protein with change from Baseline by visit with Ballooning sub-groups as stratification factor (ITT population)

C-reactive protein with change from Baseline by visit with Ballooning sub-groups as stratification factor (PP population)

C-reactive protein with change from Baseline by visit with Inflammation sub-groups as stratification factor (FAS population)

C-reactive protein with change from Baseline by visit with Inflammation sub-groups

as stratification factor (ITT population)

C-reactive protein with change from Baseline by visit with Inflammation sub-groups as stratification factor (PP population)

C-reactive protein with change from Baseline by visit with ALT sub-groups as stratification factor (FAS population)

C-reactive protein with change from Baseline by visit with ALT sub-groups as stratification factor (ITT population)

C-reactive protein with change from Baseline by visit with ALT sub-groups as stratification factor (PP population)

Fibrosis-4 Score with change from Baseline by visit (FAS population)

Fibrosis-4 Score with change from Baseline by visit (ITT population)

Fibrosis-4 Score with change from Baseline by visit (PP population)

Fibrosis-4 Score with change from Baseline by visit with hepatic fat fraction sub-groups as stratification factor (FAS population)

Fibrosis-4 Score with change from Baseline by visit with hepatic fat fraction sub-groups as stratification factor (ITT population)

Fibrosis-4 Score with change from Baseline by visit with hepatic fat fraction sub-groups as stratification factor (PP population)

Fibrosis-4 Score with change from Baseline by visit with HbA1c sub-groups as stratification factor (FAS population)

Fibrosis-4 Score with change from Baseline by visit with HbA1c sub-groups as stratification factor (ITT population)

Fibrosis-4 Score with change from Baseline by visit with HbA1c sub-groups as stratification factor (PP population)

Fibrosis-4 Score with change from Baseline by visit with Fibrosis sub-groups as stratification factor (FAS population)

Fibrosis-4 Score with change from Baseline by visit with Fibrosis sub-groups as stratification factor (ITT population)

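### The FIB-4 formula in SAP 7.3 divides platelets by √ALT instead of multiplying, so scores are too large by a factor equal to ALT and ALT acts in the wrong direction

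*SAP*

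**What the plan says.** SAP 7.3 (Secondary efficacy analyses) is the only place in either document that defines FIB-4. It reads "The formula is $FIB-4 = (Age * AST) / (Platelets", and the bracket then continues with a division sign and √ALT before it closes. The section gives no units and no citation, and does not say that a modified score is intended. The SAP reference list has no source for the index, and the protocol does not mention FIB-4.

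The score is used widely. SAP 7.3 says "The Fibrosis-4 Score will be calculated at each visit for which there is data" and "This score will be summarised and tabulated in the same manner as the primary endpoint". The same section puts inference for secondary endpoints on the same basis as for the primary endpoint. SAP 12 lists "Fibrosis-4 Score with change from Baseline by visit (FAS population") and repeats that table for the ITT and PP populations. It then repeats the set for each of six subgroup factors: hepatic fat fraction, HbA1c, fibrosis, ballooning, inflammation and ALT. That makes (1 + 6) × 3 = 21 tables.

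**The concern.** The brackets are explicit and balanced. A programmer who follows the SAP will compute a quantity that rises with ALT, whereas the index it is named after falls with ALT when the other terms are fixed.

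This matters here because ALT is itself an efficacy outcome. Protocol 4.2 lists mean change in ALT, the proportion of subjects with ALT in the reference range, and the proportion with a fall of at least 30%; SAP 7.3 adds ALT area under the curve. Under the written formula a fall in ALT lowers the fibrosis score by construction. Biopsy data come only from before enrolment (Protocol 7.3.13, SAP 5.2), and FIB-4 is the only fibrosis score planned after Baseline, so nothing else in the plan would expose the artefact. The values also could not be set against any published FIB-4 scale. In the tables by baseline ALT, the subgroups would differ in the score partly because of how it was calculated.

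**Working it through.** **Inputs**

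- Written formula: SAP 7.3.
- Index: Age × AST / (Platelets × √ALT). This is an assumption, the standard definition of the index the SAP names.
- ALT values of 19 and 30 IU/L: the protocol's reference limits for women and men (Protocol 4.2). ALT values of 45, 60, 64 and 100 are assumed for illustration.
- A 30% fall in ALT: the protocol's ALT responder threshold (Protocol 4.2).
- Age 50 years, AST 40 IU/L, platelets 250 × 10⁹/L: assumed. They cancel in the ratio of the two forms.

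The plan gives no numerical FIB-4 result, so there is no figure to reproduce.

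**Step 1: algebra.** Let S be the written score and F the index.

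S = (Age × AST) / (Platelets / √ALT) = Age × AST × √ALT / Platelets

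F = (Age × AST) / (Platelets × √ALT)

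S / F = √ALT × √ALT = ALT

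With the other terms fixed, S varies as ALT to the power +½ and F as ALT to the power −½.

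**Step 2: one subject.** Take ALT 64, so √ALT = 8.

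- S = 50 × 40 / (250 / 8) = 2000 / 31.25 = 64.0
- F = 50 × 40 / (250 × 8) = 2000 / 2000 = 1.00
- Ratio = 64, which is ALT.

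**Step 3: a range of ALT, other values as above**

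| ALT (IU/L) | Written S | Index F | S / F |
|---|---|---|---|
| 19 | 34.87 | 1.84 | 19 |
| 30 | 43.82 | 1.46 | 30 |
| 60 | 61.97 | 1.03 | 60 |
| 100 | 80.00 | 0.80 | 100 |

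The ratios are the same with platelets at 100 × 10⁹/L. S rises down the table while F falls, so the ordering of these four subjects is reversed. The error is therefore not a harmless change of scale. The factor differs between subjects and between visits, so neither a test on means nor a rank test on S gives the result that F would give.

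**Step 4: change over time**

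- ALT falls 30%, AST unchanged: S is multiplied by √0.7 = 0.837 (a 16% fall); F by 1/√0.7 = 1.195 (a 20% rise). In the example, ALT going from 64 to 45 takes S from 64.0 to 53.7 and F from 1.00 to 1.19.
- ALT and AST both fall 30%: S is multiplied by 0.7 × √0.7 = 0.586 (a 41% fall, 64.0 to 37.5); F by 0.7 / √0.7 = 0.837 (a 16% fall, 1.00 to 0.84).

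So a change in ALT alone reverses direction, and a joint enzyme response keeps its direction but is overstated.

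**The case against.** Four points can be made for the plan.

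1. **The standard definition is not in the documents.** This is true. Only the position of √ALT in the numerator follows from the SAP text alone; the factor of ALT and the reversed direction also need the definition. But the SAP uses the name of an established index and signals no modification, and a nested quotient would be an odd way to put a term in the numerator on purpose. The dependence has to be stated; it does not remove the problem.

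2. **The operator may have been altered when the PDF was read.** This cannot be excluded, and the source page should be checked. Nothing points to it, though: the formula is complete, and the multiplication sign between age and AST in the same line came through correctly.

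3. **The consequence can be overstated.** This stands in part. The reversed direction is the partial effect of ALT at fixed age, AST and platelets. Age, AST and platelets enter both forms in the same way, so the written score does not merely restate ALT. When both enzymes fall together, both forms fall. Inflation also requires ALT above 1. SAP 7.3 gives no units, and the rule in SAP 8.5, "If multiple units are reported in the eCRF, values will be transformed to SI units prior to summary", is written for the biochemistry summaries. The protocol quotes ALT in IU/L, where values are well above 1.

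4. **FIB-4 is peripheral.** It is not a protocol endpoint, carries no decision rule, and can be recalculated at any time because ALT, AST and platelets are collected (Protocol 7.3.6, Table 3). This limits the importance of the point, but a formula that is wrong as written still yields wrong tables if followed.

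**Conclusion.** The concern holds. As written, the SAP's score exceeds FIB-4 by a factor equal to the subject's ALT at that visit, and it moves with ALT in the opposite direction when the other terms are held fixed. A joint 30% fall in ALT and AST would appear as a 41% improvement instead of 16%. All 21 listed FIB-4 tables would carry a mislabelled score.

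The conclusion rests on three things: the standard definition of the index, ALT measured in IU/L, and the formula having been read correctly from the PDF. The primary endpoint, the sample size and the alpha levels are untouched. It should be corrected because the score bears the name of a fibrosis index, is analysed like the primary endpoint, and is driven the wrong way by an enzyme the trial aims to lower.

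**What to change.** Check the formula on the SAP's source page. Then amend SAP 7.3 to read FIB-4 = (Age [years] × AST [U/L]) / (Platelets [10⁹/L] × √ALT [U/L]), and add a citation for the index to the SAP reference list. State that these units apply to FIB-4 whatever conversion is used for the laboratory summaries in SAP 8.5. Program every FIB-4 table listed in SAP 12 from the corrected line, and rerun any FIB-4 output already produced with the written form.

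The cost is one line in the SAP and one in the program. No new data are needed and study conduct does not change.

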7.4 Exploratory efficacy analyses

Biomarkers, lipopolysaccharides (LPS), C-reactive protein, cytokeratin-18 fragments, C-reactive protein, PBMCs and numerous other compounds will be summarised with change from Baseline and tabulated by visit and treatment group in order to assess the effect of the treatment on the innate immunity of the body.

Serum metabolomics and gut microbiome are indicated in the protocol as being exploratory endpoints, but no additional detail was provided. Any additional analysis will be explained in full in the final study report.

Regulatory T cells will be summarised with change from Baseline and tabulated by visit and treatment group.

The gut microbiome will also be characterised by study treatment and Baseline hepatic fat fraction category in order to assess the effect of the treatment on the adaptive immunity of the body. This analysis may be performed by a different supplier.

Some endpoints will be explored for dose effects, and further ad-hoc analyses may be performed as required by the sponsor or regulatory bodies.

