**Exploratory endpoints:**

- Mean serum concentrations of: LPS, CK-18 fragments and adiponectin and subsets of cytokines IL6, IL-1 $\alpha$ , IL1 $\beta$ , IL-2, IL-3, IL-4 IL-10, IL-13, IL-12, IL-17 $\alpha$ , IL-23, IFN $\gamma$  TGF $\beta$  and TNF $\alpha$
- Serum metabolomics
- Relative levels of regulatory T cells in PBMC samples, including CD4, CD8, CD25, FoxP3, NKT and CD62
- Characterization of the gut microbiome.
- Explore a dose effect

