## 14. Concurrent medications including:

- Anti-NASH therapy(s) taken for more than 10 continuous days in the last 3 months. These include S-adenosyl methionine (SAM-e), betaine, milk thistle, bacterial probiotic supplements (other than yoghurt or other natural food sources), vitamin E and gemfibrozil.
  - NOTE: If determinant biopsy is performed while on stable treatment – subject is eligible;
  - Wash out for any of the anti-NASH therapies is as follow: under 10 days no washout required, more than 10 days and up to 3 months treatment requires 6 weeks washout. Any treatment of over 3 months would require to re-biopsy to ensure histological eligibility
  - Thiazolidinediones (glitazones), dipeptidyl peptidase 4 inhibitors (gliptins) or glucagon-like peptide-1 analogs in the last 6 months.  
NOTE: if determinant biopsy is performed while on stable treatment of at least 6 months – subject is eligible.
  - NOTE: Allowable anti-diabetic treatment includes metformin and/or sulfonylureas administered at constant dose for at least 2 months prior to study entry
  - NOTE: Subjects treated with Insulin are eligible if clinically stable on insulin treatment (i.e. no recurrent acute hypo-/hyperglycemic episodes diagnosed clinically and by Glucose serum levels of <50 mg/dL and >200 mg/dL respectively) for at least 2 months prior to study entry
- immune modulatory agents including:
  - Within 3 months of study entry:
    - systemic steroids for more than 7 days
    - daily treatment with multiple non-steroidal anti-inflammatory drugs (such as aspirin >100mg/day, ibuprofen, naproxen, meloxicam, celecoxib) for more than 1 month
  - In the last 12 months:
    - azathioprine, 6-mercaptopurine, methotrexate, cyclosporin, anti-TNF $\alpha$  therapies (infliximab, adalimumab, etanercept) or anti-integrin therapies (namixilab)
- more than 10 consecutive days oral or parenteral antibiotics within 4 weeks prior to study entry NOTE: subjects administered with antibiotics for more the 5 days prior to study entry would not be included in the stool and PBMC analysis)
- Variable dose of anti-lipidemic agents (HMG Co-A reductase inhibitors – “statins”) in the 3 months prior to Screening

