### 7.3.9 Biomarkers

Blood samples will be taken to prepare serum aliquots for measurement of biomarkers relevant to steatohepatitis. At least 3 aliquots of 1 mL of serum will be collected at Baseline, W4, W12 and W24 (see Table 5) and stored at  $\leq -70^{\circ}\text{C}$  for biomarker evaluation including serum cytokine concentrations and other markers of immunological response. C-peptide and C-reactive protein analysis will be included in addition to a standard clinical chemistry panel at Baseline, W4, W12 and W24.

In addition, PBMCs will be collected at Baseline, W12 and W24 from patients recruited at selected sites and for whom stool samples will also be collected for microbiome analysis. Details regarding the required method of collection, preparation and storage of PBMCs will be included in the Study Reference Manual.

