Correlations between change in hepatic fat fraction and ALT, AST, C-reactive protein, A1c and LPS with Ballooning sub-groups as stratification factor (FAS population)

population)

Correlations between change in hepatic fat fraction and ALT, AST, C-reactive protein, A1c and LPS with Ballooning sub-groups as stratification factor (ITT population)

Correlations between change in hepatic fat fraction and ALT, AST, C-reactive protein, A1c and LPS with Ballooning sub-groups as stratification factor (PP population)

Correlations between change in hepatic fat fraction and ALT, AST, C-reactive protein, A1c and LPS with Inflammation sub-groups as stratification factor (FAS population)

Correlations between change in hepatic fat fraction and ALT, AST, C-reactive protein, A1c and LPS with Inflammation sub-groups as stratification factor (ITT population)

Correlations between change in hepatic fat fraction and ALT, AST, C-reactive protein, A1c and LPS with Inflammation sub-groups as stratification factor (PP population)

Correlations between change in hepatic fat fraction and ALT, AST, C-reactive protein, A1c and LPS with ALT sub-groups as stratification factor (FAS population)

Correlations between change in hepatic fat fraction and ALT, AST, C-reactive protein, A1c and LPS with ALT sub-groups as stratification factor (ITT population)

Correlations between change in hepatic fat fraction and ALT, AST, C-reactive protein, A1c and LPS with ALT sub-groups as stratification factor (PP population)

PBMCs with change from Baseline by visit (FAS population)

PBMCs with change from Baseline by visit (ITT population)

PBMCs with change from Baseline by visit (PP population)

PBMCs with change from Baseline by visit with hepatic fat fraction sub-groups as stratification factor (FAS population)

PBMCs with change from Baseline by visit with hepatic fat fraction sub-groups as stratification factor (ITT population)

PBMCs with change from Baseline by visit with hepatic fat fraction sub-groups as stratification factor (PP population)

PBMCs with change from Baseline by visit with HbA1c sub-groups as stratification factor (FAS population)

PBMCs with change from Baseline by visit with HbA1c sub-groups as stratification factor (ITT population)

PBMCs with change from Baseline by visit with HbA1c sub-groups as stratification factor (PP population)

PBMCs with change from Baseline by visit with Fibrosis sub-groups as stratification factor (FAS population)

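### The SAP does not carry over the protocol's rule that keeps subjects with more than 5 days of antibiotics before entry out of the stool and PBMC analysis

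*SAP*

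**What the plan says.** **Protocol.** Section 6.3, item 14, excludes from the trial anyone with "more than 10 consecutive days oral or parenteral antibiotics within 4 weeks prior to study entry". A note to the same item adds that "subjects administered with antibiotics for more the 5 days prior to study entry would not be included in the stool and PBMC analysis". The synopsis repeats both. Section 4.2 lists the exploratory endpoint "Relative levels of regulatory T cells in PBMC samples, including CD4, CD8, CD25, FoxP3, NKT and CD62", so regulatory T cells are a PBMC readout. Section 7.3.9 says "PBMCs will be collected at Baseline, W12 and W24 from patients recruited at selected sites", and that the same patients supply stool for the microbiome.

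**SAP.** Section 3 states that the plan is based on protocol version 1.3. Section 3.1 defines the Safety, ET, ITT, FAS and PP populations; none mentions antibiotics, and there is no set for PBMC or stool. Section 7.4 says "Regulatory T cells will be summarised with change from Baseline and tabulated by visit and treatment group". For stool it says "The gut microbiome will also be characterised by study treatment and Baseline hepatic fat fraction category", adds that another supplier may do this work, and remarks: "Serum metabolomics and gut microbiome are indicated in the protocol as being exploratory endpoints, but no additional detail was provided". In section 12 the first PBMC title opens "PBMCs with change from Baseline by visit (FAS population". The same title follows for ITT and PP, and all three are repeated for each of six subgroup factors.

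**The concern.** The protocol sets a group of eligible subjects aside from two laboratory analyses, and the SAP gives the programmer no means of doing so. These are the analyses closest to the proposed mechanism, which protocol section 3.5 describes in terms of gut bacteria, LPS and regulatory T cells. A subject who enters soon after a course of antibiotics may have a disturbed Baseline sample. The change from Baseline could then contain recovery as well as any effect of treatment.

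At stake is how far the within-arm changes can be read as drug effects, in a subset of sites whose size the documents do not give. There is also a matter of record: the protocol and SAP differ, and the SAP does not say so.

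**Working it through.** The documents give no sample size, power or error rate for the PBMC or stool analyses, so there is no planned figure to reproduce. The check is a comparison of the texts, followed by an illustration under stated assumptions.

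**1. Who is eligible but barred.** More than 10 consecutive days within 4 weeks excludes from the trial; more than 5 days bars from the stool and PBMC analysis. The group in between is mainly courses of 6 to 10 days. Its edge is not sharp, because the note gives no look-back window.

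**2. Whether a SAP population applies the rule.**
- FAS: no. It takes every dosed subject, and the only permitted exclusion is documented absence of dosing.
- ITT: no. It takes every randomised subject, and it is tested only if someone was randomised but not dosed.
- PP: not by itself. Failing an eligibility criterion is one of its examples of a major violation, but a course of 6 to 10 days does not fail eligibility.

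**3. Which outputs are affected.** The PBMC tables number 3 overall (FAS, ITT, PP) plus 6 subgroup factors × 3 populations = 18, so 21 in all. None carries a restriction.

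**4. Stool.** Section 12 lists no microbiome table and section 7.4 names no population. The only link to FAS, ITT and PP is the general statement in section 7.3 that inference for sections 7.3 and 7.4 follows the basis of the primary endpoint. The SAP's remark that the protocol gave no further detail overlooks the antibiotic note.

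**5. Illustration.** None of these inputs is in the documents. Assume that a share f = 5 to 20% of sampled subjects had a barred course, that recovery shifts their change score by d = 0.5 to 1 SD, and that n = 10 to 40 subjects per arm are sampled.
- Shift in the within-arm mean change, f × d: 0.05 × 0.5 = 0.025 SD to 0.20 × 1 = 0.20 SD.
- Variance inflation, 1 + f(1 − f)d²: 1 + 0.05 × 0.95 × 0.25 = 1.012 to 1 + 0.20 × 0.80 × 1 = 1.16.
- SD of the chance between-arm difference, d√(2f(1 − f)/n): 0.5 × √(2 × 0.05 × 0.95/40) = 0.024 SD to 1 × √(2 × 0.20 × 0.80/10) = 0.179 SD.
- Subjects removed per arm by the rule, n × f: 10 × 0.05 = 0.5 to 40 × 0.20 = 8.

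For scale, the ordinary standard error of a between-arm difference with 10 per arm is √(2/10) = 0.447 SD. The worst corner raises it to √(0.447² + 0.179²) = 0.48 SD.

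**The case against.** The strongest defence is that the note stands among the eligibility criteria and could be an operational rule: these subjects would simply not be sampled or assayed, and a table on FAS would then never contain them. The SAP also finalises its populations at the Clean File meeting before unblinding (section 3.4) and sends changes from the protocol to the study report (section 10). This does not settle the matter. Protocol sections 7.3.9 and 7.3.11 put no antibiotic condition on collection, and the note speaks of analysis. Protocol section 12.4 assigns the definition of analysis populations to the SAP. Neither the Clean File meeting nor section 10 restores a rule that the SAP does not mention.

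Other parts of the defence do stand. A reader might infer that both the stool and the PBMC analyses run on the entire FAS, ITT and PP sets. The documents do not support that: for stool the SAP is silent, and a PBMC table can hold only subjects with samples from the selected sites.

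Precision alone also does not argue for exclusion. Dropping a share f multiplies the variance of a mean by 1/(1 − f). At f = 20% that is 1.25, against at most 1.16 from keeping those subjects when d is no more than 1 SD. This assumes that the treatment effect is the same in them. The case for the rule therefore rests on clean within-arm changes and on agreement between the two documents.

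**Conclusion.** The omission is real, and for PBMC and regulatory T cells it is a conflict between documents: the listed tables, run as written, would include sampled subjects whom the protocol removes. For stool the fault is an unnamed population together with an overlooked protocol rule.

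A reader might go further and conclude that antibiotic recovery is in fact mixed into these endpoints, or that the comparison between arms is biased. Neither follows. The first needs barred subjects to have been enrolled, sampled and assayed, and no count is given. On the second, antibiotic use before entry precedes randomisation, so the expected between-arm difference is zero if recovery does not depend on treatment. What remains is a possible shift in within-arm change from Baseline (0.025 to 0.20 SD on the assumptions above), some added noise, and chance imbalance in small groups. The endpoints are exploratory and the primary result is untouched, so this is a minor correction.

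**What to change.** Before unblinding, add to SAP section 3.1 a PBMC/stool evaluable set: FAS subjects with samples, minus those with more than 5 days of antibiotics before study entry, citing protocol section 6.3, item 14. State the look-back window that the note leaves open, and how antibiotics taken during the study are treated in these analyses, since protocol section 9.2.2 permits them.

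Confirm that antibiotic start and stop dates are captured. SAP section 5.4 tabulates prior medications, but protocol section 7.3.1 names only NASH medication history and concurrent medication, so the flag may not be derivable without a query to sites.

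Use the set for the PBMC, regulatory T-cell and microbiome outputs, and pass the definition to any outside supplier. Report the number excluded per arm and show the unrestricted set as a sensitivity analysis. If the sponsor prefers not to apply the rule, record and justify that as a change from the protocol.

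The cost is one definition, one derived flag and slightly fewer subjects in exploratory tables.
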